2 STATISTICAL AND ANALYTICAL PROCEDURES

The statistical analysis and reporting will be based on all data from study TDR12857 and its extension study, LTS13769. The baseline value is defined as the last non missing value prior to first TDR12857 treatment, unless otherwise specified. The rebaseline values will be the last non-missing assessment before patients switch to 20 mg/kg dose for LTS-switch patients.

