2.1.4 Safety endpoints

The safety analysis will be based on the reported adverse events (AEs) and other safety information, such as clinical laboratory data, vital signs, ECG, etc.

Observation period

The observation period will be divided into the following epochs:

- The screening epoch is defined as the study period preceding treatment, starting from the signed informed consent date (TDR12857) up to the first administration of IMP. (Note: medications known to have been taken by the patients within 28 days of the TDR12857 screening/baseline visit will be recorded in the CRF as well.)
- The treatment epoch is defined as the time from the start of the first administration of the IMP in the TDR12857 through the completion of the last administration of the IMP.
 - Before- and after-rebaseline periods within the treatment epoch will be used for select analyses
- The residual treatment epoch is defined as the time subsequent to the treatment epoch, from the completion of the last administration of the IMP through the last administration of the IMP + 28 days or the end of the protocol-defined follow-up period, whichever is earlier.

The treatment-emergent adverse event (TEAE) period will include both treatment and residual treatment epochs.

- The **posttreatment** epoch is defined as the period of time starting the day after the end of the treatment-emergent adverse event period up through the end of the study.

The on-study observation period is defined as the time from start of treatment in the TDR12857 until the end of the LTS13769 study (defined as the last follow-up visit as defined in LTS13769 protocol Section 10.1.2.9).

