The following treatment-emergent adverse event summaries will be generated for the safety population.

- Overview of treatment-emergent adverse events, summarizing number and percentage of patients and number of events with any
 - Treatment-emergent adverse event(s)
 - Severe treatment-emergent adverse event(s)
 - Serious treatment-emergent adverse event(s)
 - Treatment-emergent AESI(s)
 - IARs (protocol- and algorithm-defined)
 - Treatment-emergent adverse event(s) leading to permanent treatment discontinuation
 - Treatment-emergent adverse event leading to death
- All treatment-emergent adverse events by primary SOC, HLT, and PT, showing number (%) of patients with at least 1 treatment-emergent adverse event and number of events sorted by the SOC internationally agreed order. The other levels (HLT, and PT) will be presented in alphabetical order.
- All treatment-emergent adverse events by primary SOC and PT, showing the number (%) of patients with at least 1 treatment-emergent adverse event and number of events, sorted by the internationally agreed SOC order and by decreasing incidence of PTs within each SOC. This sorting order will be applied to all other tables, unless otherwise specified.
 - Additional summaries of before- and after-rebaseline periods will be presented for the LTS-switch group
- All treatment-emergent adverse events by PT, showing the number (%) of patients with at least 1 treatment-emergent adverse event and number of events, sorted by decreasing incidence of PTs.

- All treatment-emergent adverse events regardless of relationship and related by primary SOC and PT, showing the number (%) of patients with at least 1 treatment-emergent adverse event and number of events, sorted by the internationally agreed SOC order. The PT levels will be presented in alphabetical order.
 - Additional summaries of before- and after-rebaseline periods will be presented for the LTS-switch group
- All treatment-emergent adverse events by maximal severity, presented by primary SOC and PT, showing the number (%) of patients with at least 1 treatment-emergent adverse event and number of events by severity (ie, mild, moderate, or severe), sorted by the internationally agreed SOC order and by decreasing incidence of PTs within each SOC.
 - Additional summaries of before- and after-rebaseline periods will be presented for the LTS-switch group
- A by-patient listing of AEs, ADA, and IgE, sorted chronologically, will be presented.

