2.4.5.6 Analyses of Immunogenicity

ADA incidence and characterization

ADA status: ADA seroconversion is classified as always negative and ever positive. Baseline ADA status will be reported as negative or pre-existing ADA at initiation of treatment.

The following incidence rates will be summarized descriptively for each treatment group:

- ADA prevalence rate, defined as
$$100 \times (\text{number of patients with treatment-induced ADA} + \text{pre-existing ADA}) / (\text{number of evaluable patients})$$
- Treatment emergent ADA incidence, defined as
$$100 \times (\text{treatment boosted} + \text{treatment induced ADA positive patients}) / (\text{number of evaluable patients}),$$
- Treatment induced ADA incidence, defined as,
$$100 \times (\text{treatment induced ADA positive patients}) / (\text{number of evaluable patients with ADA negative at baseline}),$$
- Treatment boosted ADA incidence, defined as

100 x (treatment boosted ADA positive patients)/(number of evaluable patients with ADA positive at baseline).

Duration of ADA

The kinetics and duration of the immune responses will be analyzed as follow:

- Onset time of ADA will be analyzed descriptively using summary statistics minimum, Q1, median, Q3 and maximum.
- Duration of ADA will be analyzed descriptively using summary statistics minimum, Q1, median, Q3 and maximum. It will only be calculated for the patients with at least two ADA positive samples. The median duration and the quartiles will be reported.

ADA titers

- ADA peak titer, last titer, and geometric mean titer will be summarized.
- Graphs of ADA titer over time and boxplots of the highest post-baseline ADA titer will be provided.

ADA Response Classification

Response type classification will be provided.

- The number and percent of transient ADA response will be summarized descriptively. This will be performed for the patients with at least two post baseline samples where the last sampling timepoint is negative.
- The number and percent of persistent ADA response and its subclassifications will be summarized descriptively. This will be performed for the patients with treatment-induced ADA detected at two or more sampling time points post-baseline.
- The number and percent of indeterminate ADA response will be summarized descriptively. This will be performed for the patients with at least one post baseline sample.

Neutralizing ADA

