To evaluate the effect of ADA and NAb on AEs, the number and percentage of patients experiencing any TEAEs, any treatment-emergent SAEs, or any IARs, hypersensitivity (narrow SMQ), and Anaphylactic reaction (narrow SMQ) will be presented by the following sub-categories: 1. ADA status (ever positive, always negative) 2. ADA peak titer category (always negative, peak titer 100-800, 1600-6400, $\geq 12,800$) 3. ADA response type (always negative, transient response (if occur), and persistent responses subcategories: low response, intermediate response, high ADA response and tolerized at defined timepoints. 4. Correlation of frequency of IAR and ADA peak titer. 5. Neutralizing antibody status (always negative, ever positive).

Association of ADA with selected efficacy

Correlation analysis will be performed between immunogenicity (ADA titers, response categories and neutralizing ADA) and FVC, 6MWT, (raw and percent predicted), MIP, MEP.

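### Comparing adverse-event percentages by ever-positive versus always-negative ADA status can show an ADA association when there is none, because follow-up is unequal

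*SAP*

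**What the plan says.** SAP 2.4.5.6 (Evaluation of ADA on Relevant Safety Parameters) states its aim as "To evaluate the effect of ADA and NAb on AEs". The measure is "the number and percentage of patients experiencing any TEAEs, any treatment-emergent SAEs, or any IARs", plus hypersensitivity and anaphylactic reaction by narrow SMQ. The first grouping is "ADA status (ever positive, always negative"; the others are peak titer category, response type and neutralizing-antibody status. ADA status is a whole-study label: "ADA seroconversion is classified as always negative and ever positive".

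The event window does not depend on ADA onset. SAP 2.1.4 says "The treatment epoch is defined as the time from the start of the first administration of the IMP in the TDR12857" through the last dose, and "The treatment-emergent adverse event (TEAE) period will include both treatment and residual treatment epochs".

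Follow-up differs widely between patients. SAP 2 says "The statistical analysis and reporting will be based on all data from study TDR12857 and its extension study, LTS13769". The exposure categories in SAP 2.4.3.1 run from under 6 months to 6 years or more. Appendix B has a day-273 cutoff for patients who did not enter the extension, while its last windows end at day 2402. One reportable post-baseline sample puts a patient in the ADA evaluable set (SAP 2.3.4). No rate per patient-year, landmark or time-varying status is planned for this table.

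**The concern.** A patient needs time under observation both to seroconvert and to have an event. Someone who leaves at six months has had little chance of either and tends to fall among the always negative without an event. Someone followed for six years has had ample chance of both. The two percentages then differ because the groups were watched for different lengths of time.

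The table also credits to the ever-positive class any event that came before the first positive sample. That puts the event on the wrong side of seroconversion, so the table cannot show time order.

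Safety, including immunogenicity, is the primary endpoint (protocol 9.1). A table introduced as evaluating an effect will be read as doing so. The same problem reaches the titer, response-type and neutralizing-antibody rows.

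**Working it through.** The documents give no event rate, seroconversion rate or discontinuation rate for this comparison, so there is no planned figure to reproduce. The check asks what the table shows when ADA has no effect on events.

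**Inputs from the documents.** Maximum follow-up T = 2402/365 = 6.58 years (SAP Appendix B). ADA sampling is monthly for 6 months, then every 3 months (protocol 9.1.7).

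**Assumed inputs, with ranges.** Share able to seroconvert, p: 60–100%. Median time to seroconversion: 0.25, 1 or 2 years, with hazard s = ln 2/median. Discontinuation hazard d: 0 to 0.20 per year. First-event hazard h: 0.05, 0.15 or 2 per year.

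**Step 1: equal follow-up (d = 0).** Both classes have 1 − exp(−hT). With h = 0.15 this is 1 − exp(−0.987) = 62.7% in each. Simulation with detection at the sampling visits gave 62.7% v 63.0%, and 62.9% v 62.3% with slow seroconversion (median 2 years). In those two runs 9% and 42% of the ever-positive group's first events preceded detection, yet the ratios were 1.00 and 1.01. Counting early events does not by itself separate the groups.

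**Step 2: unequal follow-up.** Take p = 0.9, median 1 year (s = 0.693), d = 0.10, h = 0.15, k = d + h = 0.25.

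- Ever positive: A = p·s/(s+d)·(1 − e^(−(s+d)T)) = 0.9 × 0.874 × 0.995 = 0.782
- Ever positive, no event: B = p·[(d/k)·s/(s+k)·(1 − e^(−(s+k)T)) + (h/k)·e^(−kT)·(1 − e^(−sT))] = 0.9 × [0.293 + 0.115] = 0.367
- Any event: C = (h/k)(1 − e^(−kT)) = 0.6 × 0.807 = 0.484
- Event percentage, ever positive: 1 − B/A = 53%
- Event percentage, always negative: (C − (A − B))/(1 − A) = 0.069/0.218 = 32%

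The ratio is about 1.67 with no ADA effect. Simulation with detection at the visits gave 53.2% v 31.6%, ratio 1.68. Mean follow-up was 5.4 v 3.0 years, and 31% of the ever-positive group's first events preceded detection.

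**Step 3: range (simulated, no ADA effect).**

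| Setting | Ever positive | Always negative | Ratio |
|---|---|---|---|
| p 0.9, median 0.25 y, d 0.10, h 0.15 | 50.1% | 37.5% | 1.34 |
| p 0.9, median 1 y, d 0.20, h 0.05 | 19.5% | 9.0% | 2.17 |
| p 0.6, median 0.25 y, d 0.10, h 0.15 | 50.3% | 46.0% | 1.09 |
| p 0.6, median 1 y, d 0.10, h 0.15 | 53.0% | 43.1% | 1.23 |
| p 0.9, median 0.25 y, d 0.05, h 0.15, 20% stop at 6 months | 48.4% | 30.4% | 1.59 |
| p 0.9, median 1 y, d 0.05, h 0.15, half of events end treatment | 53.6% | 58.3% | 0.92 |

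With p = 0.9 and d from 0.05 to 0.20, the ratio ran from 1.11 to 2.17. For very common events (h = 2, closest to any TEAE) a ceiling held it to about 1.1–1.35. If 20% of events ended treatment it was 1.08–1.14; if 50% did, 0.92–0.97. If everyone can seroconvert and 20% stop at 6 months, it ran from 1.6 to 9.1, because the always-negative group is then almost only short-stay patients. That extreme is outside the headline range.

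**Step 4: which remedy works.** Dividing the ever and never groups by patient-years gave 0.98–1.01 when discontinuation was unrelated to events, but 0.50–0.84 when 20–50% of events ended treatment. Splitting each patient's time at the first positive sample gave 0.99–1.02 throughout, at a constant hazard. If the event hazard is 3–4 times higher in the first 6 months, the plain split gave 0.49–0.64, a false protective effect, because ADA-negative time is mostly early time. Stratifying the split by time on treatment restored 0.99–1.00.

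**The case against.** The safety analyses are descriptive, with no systematic testing (SAP 2.4.5), and the SAP says elsewhere that patients are few. Time order can be followed: "A by-patient listing of AEs, ADA, and IgE, sorted chronologically, will be presented". ADA onset is summarized, and the IAR listing gives timing from first infusion. In a small study, reading cases one by one is reasonable.

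This lowers the weight of the point but does not remove it. A listing does not correct a percentage, the Kaplan-Meier table of TEAEs is not described as being by ADA status, and SAP 2.4.5 allows relative risks between groups where relevant. For PK, the same SAP section already uses titer category at the time of assessment, so the principle is not foreign to the plan.

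Three stronger readings are tempting and are not supported:

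- A reader might infer that counting events before seroconversion is what makes the false association. Step 1 shows it is not; unequal follow-up is.
- A reader might infer that the bias always points towards harm. Its direction depends on why patients leave, which the documents do not tell us.
- A reader might infer that the persistent class requires long follow-up by definition. SAP 2.1.4.6 also accepts positives at the last two samplings, however close together.

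**Conclusion.** The concern holds in a limited form. The planned comparison can produce an ADA–event association with no underlying effect, and it cannot serve its stated aim. Under the assumed rates the ratio of percentages is about 1.1 to 2.2, near 1.0 if follow-up is equal, and possibly below 1 if adverse events often end treatment. These sizes rest on assumed seroconversion, discontinuation and event rates; the real bias may be small if nearly all patients entered and stayed in the extension. The table is acceptable as description, but not as an estimate of what ADA does.

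**What to change.** Keep the table and make two additions to SAP 2.4.5.6.

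1. Show follow-up duration for each ADA and neutralizing-antibody class beside the percentages, and state that the percentages do not estimate an effect of ADA.
2. Add one analysis that respects time order. Either treat ADA (and neutralizing-antibody) status as time-varying, splitting each patient's time at the first positive sample and stratifying by time on treatment (for example 0–3, 3–6 and 6–12 months, 1–2 years, over 2 years). Or use a landmark: classify patients by status at a fixed visit, such as Month 6 of LTS13769, and count later events only. Patients positive at baseline contribute only ADA-positive time.

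Count time to first event per patient, or reaction episodes per infusion, and not raw AE terms. Protocol 10.4.2 has each sign or symptom of an IAR, allergic or anaphylactic reaction entered as its own AE term, so a term-based rate would be driven by symptom counts in a few patients.

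The cost is a SAP paragraph and a derived status flag from dates already collected. The downsides are sparse cells in a small study, a seroconversion date known only to within the 1–3 month sampling interval, and, for a Month 6 landmark, the loss of patients who never entered the extension.

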9.1.7 Immunogenicity

Immunogenicity assessments will include the following:

- Samples will be collected from patients and evaluated for anti-avalglucosidase alfa antibodies every month during the first 6 months and then every 3 months throughout the duration of the study. ADA seropositive patient serum will be assessed for neutralizing antibodies to avalglucosidase alfa which may include inhibition of enzyme activity and uptake.
- Samples will be collected from patients who were previously treated with alglucosidase alfa and evaluated for anti-alglucosidase alfa IgG antibodies every 6 months for up to the first 6 years of the study.
- Samples will be collected from patients and evaluated for IgE, complement activation, serum tryptase following moderate, severe, or recurrent mild IARs suggestive of hypersensitivity reactions ([Section 8.8.2](#)).
- In the event a patient exhibits signs or symptoms suggestive of systemic immune-mediated reactions involving skin and other organs while receiving alglucosidase alfa, serum samples are obtained for the evaluation of circulating immune complexes.
- Leftover antibody samples will be stored for further analysis as needed.
- See the study-specific laboratory manual as well as the Study Operations Manual (SOM) for guidelines on the collection and shipment of antibody and IAR samples and circulating immune complex samples.

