2.1.4.6 Anti-drug antibody and neutralizing antibody endpoints

Patients will be tested for anti-avalglucosidase alfa antibodies. Samples will be collected from patients for evaluation of ADA. ADA seropositive patient serum will be assessed for neutralizing antibodies to avalglucosidase alfa, including inhibition of enzyme activity and uptake.

The qualitative sample status of the ADA will be assessed and be categorized into the following classes:

- ADA-negative sample: a sample is considered negative if ADAs are not detected (ie, negative in screening assay or reactive in screening but negative in confirmatory assay).
- ADA-positive sample: sample in which ADA is detected, ie, sample generates an assay signal equal to or greater than the cut-point in the screening assay and is tested positive in the confirmatory assay.

The ADA titer of the positive samples will also be assessed. A titer represents a quasi-quantitative information on the level of ADA present in a sample. Confirmed positive samples are serially diluted until a negative result is achieved. The titer is subsequently defined as the reciprocal of the last dilution that tests positive. The minimal required dilution (MRD) will be incorporated in the final calculation.

The ADA attributes will be determined by the following conditions :

- Pre-existing ADAs: antibodies reactive with the study drug present in subjects before treatment.
- Treatment induced ADAs: ADAs developed de novo (seroconversion) following administration of the study drug. If the baseline ADA sample is missing or non-reportable and at least one reportable on-treatment ADA sample is available, the baseline sample will be considered as “negative”.
- Treatment boosted ADAs: Pre-existing ADAs that were boosted at least two titer steps from baseline (i.e., 4 fold increase in titers) following administration of the study drug (any time after the first drug administration).

The following kinetics of the ADAs will be analyzed:

- Onset of ADA is defined as the time period (in weeks) between the first study drug administration and the first instance of treatment induced ADAs.
- Duration of ADA will be calculated as the date of last treatment induced ADA sample minus date of first treatment induced ADA sample + 1.

The following ADA response classifications will be used:

1. Treatment-induced ADA- patients are ADA negative at baseline and have developed an ADA response

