2.4.5.1 Analyses of adverse events

Generalities

The primary focus of adverse event reporting will be on treatment-emergent adverse events. Pretreatment and posttreatment adverse events will be described separately.

If an adverse event date/time of onset (occurrence, worsening, or becoming serious) is incomplete, an imputation algorithm will be used to classify the adverse event as pretreatment, treatment-emergent, or posttreatment. The algorithm for imputing date/time of onset will be conservative and will classify an adverse event as treatment-emergent unless there is definitive information to determine it is pretreatment or posttreatment. Details on classification of adverse events with missing or partial onset dates are provided in [Section 2.5.3](#).

Adverse event incidence tables will present adverse events grouped by SOC and PT, including the number and percentage of patients experiencing AEs in each SOC/PT category and the associated event counts (see the paragraph below for sorting order). Multiple occurrences of the same event in the same patient will be counted only once in the tables within observation period presented

(pretreatment, treatment-emergent, and posttreatment). The denominator for computation of percentages is the safety population within each patient and dose group.

Sorting within tables ensures the same presentation for the set of all adverse events within the observation period (pretreatment, treatment-emergent, and posttreatment). For that purpose, the table of all treatment-emergent adverse events presented by SOC and PT sorted by the internationally agreed SOC order and decreasing frequency of PTs within SOCs will define the presentation order for all other tables unless otherwise specified. Sorting according to frequency of PTs will be based on the sum of patient counts for the patients in the 20mg/kg dose groups. In the case of the AE by maximal severity tables, the sum of patient counts for the severe AEs from patients in the 20 mg/kg dose groups will be used for the sorting of PTs.

For patients previously assigned to the 5 or 10 mg/kg dose groups in the TDR12857, entered the LTS13769 study, and switched to the 20 mg/kg dose group (LTS-switch group), additional AE summaries, as indicated in respective subsections below, will be generated for comparison of before- and after-rebaseline adverse events in these patients.

Analysis of all treatment-emergent adverse events

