- Incidence of neutralizing antibodies (inhibition of enzyme activity and inhibition of enzyme uptake) will be reported for both treatment naïve and switch patients
- Onset time of neutralizing ADA will be analyzed descriptively using summary statistics minimum, Q1, median, Q3 and maximum.
- Duration of neutralizing ADA will be analyzed descriptively using summary statistics minimum, Q1, median, Q3 and maximum. It will only be calculated for the patients with at least two ADA positive samples.

The following listings will be provided:

- Anti-avalglucosidase alfa alfa antibody titer values, neutralizing antibody, circulating immune complex, anti-avalglucosidase alfa IgE antibody, serum tryptase activity, complement activation, and skin testing performed
- Listings of anti-avalglucosidase alfa ADA and inhibitory antibodies
- Listings of anti-alglucosidase alfa ADA and inhibitory antibodies

Association of ADA with PK

The following analysis will be considered for switched patients: 1. Within Subject level AUC change from baseline to the last injection will be plotted by peak titer category. Gender will be separated by different color. 2. Between subject comparison of ADA-positive vs. ADA negative. Plot of AUC at baseline compared to timepoints where full PK assessment is available. Patients will be evaluated by titer categories based on titer category at the time of PK assessment. Patients will be separated based on treatment groups. 3. Summary table to include AUC and % change from Day 1 at each scheduled visit by peak titer categories. 4. Data will be assessed for switch patients as appropriate.

Association of ADA and PD marker

Hex-4 is a clinically relevant PD marker that is related to the drug's mechanism of action. Summary table of number (%) of patients with elevated urinary hex-4 by titer value at the specified visit (eg, peak titer categories) over time will be provided.

Evaluation of ADA on Relevant Safety Parameters

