2.5.3 Missing data

No imputation (single or multiple) is planned for this study.

For categorical variables, patients with missing data are not included in calculations of percentages unless otherwise specified. When relevant, the number and percentage of patients with missing data is presented.

Handling of computation of treatment duration if investigational medicinal product end of treatment date is missing

For the calculation of the treatment duration, the date of the last dose of IMP is equal to the date of last administration reported on the end-of-treatment CRF page. If this date is missing, the exposure duration should be left as missing.

The last dose intake should be clearly identified in the CRF and should not be approximated by the last returned package date.

Handling of medication missing/partial dates

No imputation of medication start/end dates or times will be performed. If a medication date or time is missing or partially missing and it cannot be determined whether it was taken prior or concomitantly, it will be considered a prior, concomitant, and posttreatment medication.

Handling of adverse events with missing or partial date/time of onset

Missing or partial adverse event onset dates and times will be imputed so that if the partial adverse event onset date/time information does not indicate that the adverse event started prior to treatment or after the treatment-emergent adverse event period, the adverse event will be classified as treatment-emergent. No imputation of adverse event end dates/times will be performed. These data imputations are for categorization purpose only and will not be used in listings. No imputation is planned for date/time of adverse event resolution.

Handling of adverse events when date and time of first investigational medicinal product administration is missing

When the date and time of the first IMP administration is missing, all adverse events that occurred on or after the day of randomization should be considered as treatment-emergent adverse events. The exposure duration should be kept as missing.

The last dose intake should be clearly identified in the CRF and should not be approximated by the last returned package date.

Handling of missing assessment of relationship of adverse events to investigational medicinal product

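### The SAP does not say where never-ADA patients go in the NAb safety comparison, and it admits patients to the NAb-duration summary on ADA-positive rather than NAb-positive samples

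*SAP*

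**What the plan says.** **Who is tested.** Both documents limit NAb testing to ADA-positive patients. SAP 2.1.4.6: "ADA seropositive patient serum will be assessed for neutralizing antibodies to avalglucosidase alfa, including inhibition of enzyme activity and uptake". Protocol 9.1.7: "ADA seropositive patient serum will be assessed for neutralizing antibodies to avalglucosidase alfa which may include inhibition of enzyme activity and uptake".

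**What is tabulated.** SAP 2.4.5.6, under the evaluation of ADA on safety parameters, opens with "To evaluate the effect of ADA and NAb on AEs, the number and percentage of patients experiencing any TEAEs" and goes on to serious events, infusion-associated reactions, hypersensitivity and anaphylaxis. Five breakdowns follow. The first three use ADA status, peak titer and response type; the fifth is "Neutralizing antibody status (always negative, ever positive". It has two levels, none for untested patients, and no stated denominator.

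**General rules that could fill the gap.** SAP 2.4.5.1, for adverse-event incidence tables: "The denominator for computation of percentages is the safety population within each patient and dose group". SAP 2.5.3: "For categorical variables, patients with missing data are not included in calculations of percentages unless otherwise specified".

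**NAb duration.** The part of SAP 2.4.5.6 on neutralizing ADA plans a summary of NAb duration and adds: "It will only be calculated for the patients with at least two ADA positive samples". The same condition is given for ADA duration earlier in that section. The only duration formula, in SAP 2.1.4.6, is written for treatment-induced ADA samples: last date minus first date plus 1. NAb has no formula of its own.

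**The concern.** Because only ADA-positive serum is assayed, every NAb-positive patient is also ADA-positive. If never-ADA patients count as NAb *always negative*, that class combines people who made no antibody with people whose antibody did not neutralize. The comparison with NAb *ever positive* then carries any ADA effect with it. Neutralization could appear to raise the risk of reactions when it adds nothing beyond ADA positivity. If never-ADA patients are left out, the problem does not arise. Two programmers following the same SAP could produce different tables, and a reader could not tell from the SAP which one was intended.

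Immunogenicity is among the safety assessments that make up the primary endpoint (protocol 9.1), and SAP 2.4.5 allows relative risks with 95% confidence intervals between groups, so the class definition matters.

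The duration rule is a separate matter. Requiring two positive samples stops a single positive from entering as a 1-day duration. When the samples counted are ADA-positive but the duration is that of NAb, the rule no longer does this.

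**Working it through.** **1. Which reading applies?** The plan has no figure to reproduce here: it gives no ADA rate, NAb rate, event risk or sample-size calculation. The wording has to be weighed.

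- For pooling: the 2.4.5.1 denominator includes never-ADA patients. The first three breakdowns use *always negative* for patients who never had ADA, and the fifth reuses the label without restriction. Elsewhere in 2.4.5.6 restricted denominators are spelled out, for example for treatment-induced ADA incidence.
- For exclusion: a never-ADA patient has no NAb result, and under 2.5.3 patients with missing categorical data drop out of percentages. The 2.4.5.1 rule is framed for patient and dose groups, not antibody subgroups.

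Neither reading is stated.

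**2. What would pooling do?** Let f0 be the share of patients never ADA-positive, f1 the share ADA-positive and never NAb-positive, and f2 the share NAb-positive. Suppose risk depends on ADA only: r0 without ADA, r1 with ADA, whatever the NAb result.

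- Pooled *always negative* risk = (f0·r0 + f1·r1)/(f0 + f1)
- Spurious NAb difference = (r1 − r0)·f0/(f0 + f1)

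All inputs are assumptions. Example: f0 = 20% and NAb positivity among ADA-positives 30% give f2 = 0.80 × 0.30 = 24% and f1 = 56%. With r0 = 10% and r1 = 40%, the pooled risk is (0.20 × 0.10 + 0.56 × 0.40)/0.76 = 32.1%. The spurious difference is 40 − 32.1 = 7.9 points, relative risk 1.25.

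Spurious difference in percentage points, by assumed risks (r0 v r1):

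| Never ADA+ | NAb+ among ADA+ | Untested share of pooled class | 10% v 40% | 20% v 40% | 10% v 20% |
|---|---|---|---|---|---|
| 5% | 30% | 7.0% | 2.1 | 1.4 | 0.7 |
| 10% | 30% | 13.7% | 4.1 | 2.7 | 1.4 |
| 20% | 30% | 26.3% | 7.9 | 5.3 | 2.6 |
| 40% | 30% | 48.8% | 14.6 | 9.8 | 4.9 |
| 20% | 60% | 38.5% | 11.5 | 7.7 | 3.8 |
| 40% | 60% | 62.5% | 18.8 | 12.5 | 6.3 |

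The range is 0.7 to 18.8 points (relative risk 1.04 to 1.88). Among ADA-positive patients only, both sides have risk r1 and the difference is 0 in every row.

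**3. NAb duration.** Take a patient with at least two ADA-positive samples, who therefore meets the stated condition, and apply the ADA formula to NAb-positive dates:

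- no NAb-positive sample: qualifies, but there are no dates and nothing to calculate;
- one NAb-positive sample: last = first, so 0 + 1 = 1 day;
- two or more: last − first + 1, as intended.

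After the first six months, scheduled ADA sampling in the extension's treatment phase is three-monthly (protocol 9.1.7). A 1-day value there reflects having a single positive sample, not a measured duration.

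**The case against.** A reader might infer that the SAP pools never-ADA patients into NAb *always negative*, that the comparison is therefore confounded by design, and that the table will report a false NAb effect. The documents do not support this. The category is undefined, *always negative* on an assay can mean tested and negative, and the missing-data rule gives a route to exclusion. Confounding is a consequence of one reading, not a stated plan.

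The likely harm is also limited. SAP 2.4.5 calls the safety analysis essentially descriptive with no systematic testing. The same events are tabulated by ADA status. Since NAb-positive patients are a subset of ADA-positive patients, the ADA-positive, NAb-negative counts can be recovered by subtracting NAb *ever positive* from ADA *ever positive*, both for patients and for patients with events, provided both tables cover the same population. By-patient listings are planned as well. If few patients stay ADA-negative, the distortion is small even under pooling.

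On duration, the sentence looks carried over from the ADA paragraph. An ADA-positive patient who is never NAb-positive adds no value to the summary. The 1-day result needs the ADA formula to be borrowed, and the number of patients affected is unknown.

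All of this stands and lowers the stakes. It does not supply the missing denominator or put the duration condition on the right antibody. Subtraction also leaves the reader to rebuild the contrast the table was meant to show.

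**Conclusion.** The point holds as two gaps in definition. First, the NAb breakdown does not say whether never-ADA patients are counted as *always negative* or left out, and the SAP's general rules conflict. The effect cannot be sized from the documents. It is about 0.7 to 18.8 points if pooled, assuming an ADA-negative share of 5–40%, NAb positivity among ADA-positives of 30% or 60%, event risks of 10–20% v 20–40%, and no true NAb effect. It is 0 if the comparison is restricted to ADA-positive patients. Second, the NAb-duration condition counts ADA-positive samples, so a patient with a single NAb-positive sample can qualify, contributing 1 day under the only formula given. That follows from the text and does not depend on the pooling question. Both are worth correcting, but they concern descriptive summaries and do not undermine the main safety analysis.

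**What to change.** In SAP 2.4.5.6:

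- Replace the two-level NAb breakdown with three exclusive classes: (1) ADA always negative; (2) ADA ever positive and NAb always negative; (3) NAb ever positive. State that the NAb contrast is class 3 against class 2.
- Make the condition for NAb duration at least two NAb-positive samples, and define the duration from the first to the last NAb-positive sample.

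Leave the plot groups in SAP 2.4.6 as they are. They include a separate group with pre-existing ADA, which the three classes would lose.

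The cost is SAP wording and one extra table column, with no new data. The drawback is smaller cells in a descriptive table.
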